My Surgical Success: A Randomized Controlled Pilot Study of a Pre-surgical Psychological Intervention

Statistical Analysis Plan

NCT03076190

June 15, 2018

Statistical Analysis

Statistical Analysis All analyses were conducted using SAS9.4. For acceptability and patient-reported outcomes, group differences were tested using analyses of varaiance (ANOVAs) for numerical covariates and chi-square tests for categorical covariates. The effect of the MSS vs HE control on opioid cessation in the 12-week postsurgical follow-up period was assessed using survival analyses. The opioid stop event was considered to have occurred if the patient reported an opioid stop date and was censored otherwise. Duration to opioid cessation was computed as days from surgery to the last patient-reported date of opioid stoppage or last known patient contact (for censored observations). Product-limit survival estimates (Kaplan-Meier curves) and the log-rank test of equality of survival curves between the MSS and HE control groups were generated using PROC LIFETEST. Time to opioid cessation event was assessed using a Cox proportional hazard regression model with the experimental condition as the predictor following a supremum test of the validity of the proportionality assumption (PROC PHREG). Two follow-up analyses were conducted. First, we tested whether MSS and HE control differed in the odds of postsurgical opioid cessation (independent of duration) using a logistic regression model (PROC LOGISTIC). Second, we tested whether the median time to opioid cessation was different between the two groups using a nonparametric test of medians (PROC NPAR1WAY with the median option). For each of the psychological covariates (pain catastrophizing, pain intensity, pain interference, anxiety, depression, and physical function), we assessed the treatment effect (MSS vs HE control) as follows. We first assessed whether there was evidence of a treatment time effect in the postsurgical period (two-, four-, eight-, and 12-week follow-up), and finding none, we averaged the postsurgical measures to create a composite postsurgical measure. For each of the covariates, we then specified a mixed-design ANOVA with treatment (MSS vs HE control, between-subjects), time (pre vs post, within-subjects), and the treatment time interaction as predictors.

Power Analysis The study was designed to detect a hazard ratio of 1.9, the equivalent of a "medium" effect in terms of Cohen's d [23, 24], for the effect of the MSS treatment vs HE control in the 12-week postsurgical follow-up after surgery using Cox proportional hazards regression (PROC POWER). The analysis indicated that a total sample of 82 patients would be needed to yield a power of 0.8 and a two-tailed alpha of 0.05.

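### Read literally, the event rule codes a patient who takes no opioid after surgery as a continuing user, which can distort the powered comparison in either direction

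*SAP*

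**What the plan says.** The Statistical Analysis section fixes the event and its time in two sentences. The event: "The opioid stop event was considered to have occurred if the patient reported an opioid stop date and was censored otherwise". The time: "Duration to opioid cessation was computed as days from surgery to the last patient-reported date of opioid stoppage", with last known contact used for censored patients.

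The definition feeds the Kaplan-Meier curves, the "log-rank test of equality of survival curves between the MSS and HE control groups" and a "Cox proportional hazard regression model with the experimental condition as the predictor". A follow-up analysis asks whether the arms "differed in the odds of postsurgical opioid cessation (independent of duration) using a logistic regression model". No separate definition of cessation is given for that model, so the same event indicator is taken to apply.

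The Power Analysis section sizes the trial on the Cox comparison: hazard ratio 1.9, power 0.8, two-tailed alpha 0.05, 82 patients. A higher hazard of stopping is the better result.

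**The concern.** The word *otherwise* in the event rule is a catch-all. It puts two opposite outcomes in one category: a patient still taking opioids at week 12, and a patient who took none after the operation and so had no stop date to give. The second is the best result the outcome can show, yet it is recorded as no cessation up to last contact.

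This is not a detail left to the protocol. The SAP states the rule, and the rule decides the coding. Needing no opioid after surgery is also something a presurgical intervention could plausibly influence, so the number of patients affected may differ by arm. At stake is the one comparison for which the trial was powered.

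**Working it through.** **Reproducing the planned sample size.** Inputs from the Power Analysis section: HR 1.9, two-sided alpha 0.05, power 0.8. Allocation is not stated; 1:1 is assumed.

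- Freedman: events = (1.96 + 0.84)² × [(1.9 + 1)/(1.9 − 1)]² = 7.849 × 10.383 = 81.49, rounded up to 82.
- Schoenfeld: events = 4 × 7.849/(ln 1.9)² = 31.40/0.412 = 76.2, rounded up to 77, which needs about 93–94% of 82 patients to have the event.

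Either way, the 82 patients leave little or no room for censoring.

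**Loss of events alone.** If zero-use patients are censored, 82 patients yield at most 82 × 0.95 ≈ 78, 82 × 0.90 ≈ 74 or 82 × 0.80 ≈ 66 events at 5%, 10% or 20% zero use. Freedman power is Φ(√events × 0.9/2.9 − 1.96), giving about 0.78, 0.76 and 0.71. That is a modest loss.

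**The larger effect.** Censored zero-use patients also stay in every risk set until last contact and never have an event, which changes the estimated HR. This needs simulation.

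Assumptions, none of them in the SAP: 41 per arm; exponential times rounded up to whole days; HR 1.9 among users; control median 14 or 28 days; no dropout; zero-use patients censored at day 84 under the rule. Day-0 events were placed at half a day, ahead of all others. There were 1,500 trials per scenario (Monte Carlo error about 1.3 percentage points). HR is the median estimate; power is log-rank rejection in favour of MSS.

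| Zero use MSS/HE | Control median | Rule as written: HR, power | Day-0 event: HR, power |
|---|---|---|---|
| 0%/0% | 14 d | 1.84, 0.80 | 1.84, 0.80 |
| 0%/0% | 28 d | 1.88, 0.80 | 1.88, 0.80 |
| 5%/5% | 14 d | 1.55, 0.50 | 1.82, 0.76 |
| 5%/5% | 28 d | 1.69, 0.61 | 1.83, 0.75 |
| 10%/10% | 14 d | 1.44, 0.36 | 1.77, 0.73 |
| 10%/10% | 28 d | 1.60, 0.51 | 1.77, 0.70 |
| 10%/5% | 14 d | 1.27, 0.21 | 1.88, 0.81 |
| 10%/5% | 28 d | 1.45, 0.35 | 1.88, 0.81 |
| 15%/5% | 14 d | 1.09, 0.06 | 1.94, 0.85 |
| 15%/5% | 28 d | 1.24, 0.16 | 1.98, 0.84 |
| 5%/15% | 14 d | 1.96, 0.82 | 1.58, 0.54 |
| 5%/15% | 28 d | 2.08, 0.86 | 1.56, 0.49 |

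Analysing users only gives HR 1.87 and 1.89 and power 0.78 and 0.77 at 5%/5%. The loss therefore comes from the censoring rule and does not depend on preferring day-0 coding.

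**Time of last contact.** The rule censors at last contact, which may come before day 84. Spreading zero-use patients' last contact over weeks 2, 4, 8 and 12 (400 trials per cell) softens the 10%/5% case to HR 1.45, power 0.35 (14-day median) and HR 1.61, power 0.52 (28-day median).

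**No effect among users.** With HR 1.0 among users, a 14-day median and 15%/5% zero use, the rule gives HR 0.77 and a significant result against MSS in 20% of trials.

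**Logistic model.** Median odds ratio under the rule, against zero use counted as stopped:

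- 10%/10%, 14-day median: 1.00 against 1.00
- 10%/10%, 28-day median: 2.01 against 5.25
- 15%/5%, 14-day median: 0.42 against 1.00
- 15%/5%, 28-day median: 1.00 against 5.87

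**The case against.** The strongest objection is that the premise is not in the document. The SAP does not say that any operated patient took no opioid, whether such a patient would enter the cessation analysis, or how zero use was recorded. Eligibility, analysis set and data capture may sit in the protocol, which is not shown. If there were no such patients, or each was given a date such as the day of surgery, there is no bias. This stands, and it makes the point conditional. It does not rescue the rule, which has no exception if such patients do arise.

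A reader might infer that the rule always works against the better arm. It does not: at 5% zero use in MSS and 15% in HE, it moves the estimate in favour of MSS. A reader might also infer that the logistic result is always biased. With equal zero use and nearly all users stopping, the odds ratio is unchanged.

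The size is also sensitive to the scenario. Near-total loss of the effect requires zero use in MSS about three times that in HE. With a 56-day control median and 5% in each arm, the rule and day-0 coding agree (HR 1.82 and 1.84, power 0.64 for both).

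Finally, a reader might extend the point to negative durations in patients who stopped before surgery. The SAP mentions no presurgical users, and such a patient would have a reported date and so would not be censored. That extension has no support here.

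**Conclusion.** The point holds in conditional form. As written, the rule gives a patient with no postsurgical opioid use and no stop date the same code as a continuing user, in the powered comparison and, on the natural reading, in the logistic model. If such patients exist, the comparison can be distorted: against the better arm when zero use is equal or higher there, and in favour of MSS when zero use is clearly more common in HE.

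For control medians of 14 to 28 days, and allowing for earlier last contact:

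- 5% zero use in both arms gives HR about 1.6–1.8 and power about 0.5–0.7, against about 1.8–1.9 and 0.70–0.78 with day-0 events.
- 10% in MSS and 5% in HE gives HR about 1.3–1.6 and power about 0.2–0.5, against about 1.9 and 0.8.

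The zero-use rates, medians, time distribution and allocation are all assumptions. The document cannot establish that the trial's result was in fact biased.

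**What to change.** Add to the event definition: *Patients who report taking no opioid after surgery are counted as events at day 0 and as cessation = yes in the logistic model; all other patients without a reported stop date (still using, stopped without a date, or use unknown) are censored at the last contact.* The second clause is needed so that patients with unknown use or no date still have a rule.

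Report the number of zero-use patients by arm; if it is none, saying so settles the matter. Add a sensitivity analysis in patients with at least one postsurgical dose, labelled as a non-randomised subset, alongside a comparison of zero use between arms.

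The cost is a short addition to the SAP, a recode and one extra analysis, with no further patients, provided zero use can be identified in the data, which the SAP does not confirm. There are two drawbacks. With equal zero use, day-0 coding slightly attenuates the users' HR (1.77 at 10%/10%) and puts a point mass at day 0 in the Cox model. The SAP also describes its analyses in the past tense; if they are already done, the recode should be labelled post hoc.

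### The SAP counts an opioid stop only when a date was reported, so a known but undated stop would be analysed as continued use; how many patients this affects is not stated and may be none

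*SAP*

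**What the plan says.** The Statistical Analysis section defines the event in one sentence: it was "considered to have occurred if the patient reported an opioid stop date and was censored otherwise". The next sentence sets the time variable as "days from surgery to the last patient-reported date of opioid stoppage or last known patient contact (for censored observations".

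These two definitions feed the Kaplan-Meier curves, the log-rank test and the Cox model. A follow-up analysis asks whether the arms "differed in the odds of postsurgical opioid cessation (independent of duration) using a logistic regression model"; no separate definition of cessation is given for it.

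The Power Analysis section ties the sample size to the Cox comparison: "The study was designed to detect a hazard ratio of 1.9", with a "total sample of 82 patients would be needed to yield a power of 0.8 and a two-tailed alpha of 0.05".

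The section has no rule for a patient who reports having stopped but gives no date: no event defined by status, no imputed date and no interval censoring. Its only schedule (weeks 2, 4, 8 and 12) is given for the psychological measures.

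**The concern.** The rule is exhaustive: with a date the patient is an event, and without one the patient is censored. Consider someone who used opioids after surgery, reports at one contact that they are still using, and at the next that they have stopped but cannot say when. Cessation is known and its time is bracketed by two contacts. Under the rule this patient is a non-event at last contact, indistinguishable from one still using at that time.

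Ordinary censoring means that the event had not been seen by the censoring time. Here the patient is censored after the event took place and stays in the risk set in the meantime. A known success becomes a non-event with a long duration, in the analysis on which the trial was powered. If the logistic model uses the same flag, the patient also counts as not having ceased, although that model needs no date.

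**Working it through.** **Inputs from the SAP.** Hazard ratio (HR) 1.9, where above 1 means faster cessation under MSS; 82 patients; power 0.80; two-sided alpha 0.05; 12 weeks (84 days) of follow-up.

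**Assumed, because the SAP is silent.** 1:1 allocation (41 vs 41); exponential times; HE median 38 days; opioid contacts on days 14, 28, 56 and 84; undated share 0 to 20% of stops.

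**1. The plan's own figure.** With (1.960 + 0.842)² = 7.849:
- Freedman: 7.849 × (2.9/0.9)² = 7.849 × 10.383 = 81.5, so 82 events.
- Schoenfeld: 4 × 7.849 / (ln 1.9)² = 31.396 / 0.412 = 76.2, so 77 events; 77/82 = 94%.

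The SAP does not state the event share. The figure of 82 is reproduced if all patients have an event (Freedman) or about 94% do (Schoenfeld). Either way there is little room to lose events.

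**2. Events lost, HR held at 1.9.** Power = Φ(√d × ln 1.9 / 2 − 1.960), with d events:
- d = 82: Φ(2.906 − 1.960) = 0.828
- d = 74 (10% lost): Φ(2.761 − 1.960) = 0.788
- d = 66 (20% lost): Φ(2.607 − 1.960) = 0.741

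Losing 10% of events alone costs about 4 points of power. Keeping known stoppers at risk can cost much more.

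**3. Why the HR shrinks at equal rates.** Let S be the proportion truly still using and p the undated share, the same in both arms, with undated stoppers held to day 84. The risk set is then S + p(1 − S), and the observed HR at time t is

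1.9 × [S₁/(S₁ + p(1 − S₁))] / [S₀/(S₀ + p(1 − S₀))].

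With p = 0.10:
- Day 38: S₀ = 0.500, S₁ = 0.500^1.9 = 0.268. HR = 1.9 × 0.785/0.909 = 1.64.
- Day 84: S₀ = 0.216, S₁ = 0.054. HR = 1.9 × 0.365/0.734 = 0.95.

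The faster arm accumulates more undated stoppers, so its risk set is inflated more. The observed HR starts at 1.9 and falls with time.

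**4. Size by simulation** (Cox model, 41 vs 41, true HR 1.9).

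| Undated, both arms | Censored at | Estimated HR | Power |
|---|---|---|---|
| 0% | – | 1.90 | 0.78 |
| 2% | day 84 | 1.86 | 0.71 |
| 10% | day 84 | 1.65 | 0.53 |
| 10% | first visit after the stop | 1.87–1.91 | 0.69–0.74 |
| 20% | day 84 | 1.55 | 0.36 |
| 20% | first visit after the stop | 1.84 | 0.61 |
| 10–20% | undated stops placed at midpoint | about 1.9 | 0.73–0.78 |

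Repeat runs with no undated stops gave power of 0.73 to 0.79, so small differences in the last column should not be read closely. The 0% row can be checked by hand: expected events are 41 × (0.784 + 0.946) = 70.9, and the formula in step 2 gives Φ(2.702 − 1.960) = 0.77.

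The assumed median matters. At 10% undated, censored at day 84, the HR is 1.47 with an HE median of 14 days and 1.80 with 60 days.

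**5. Unequal rates, day-84 censoring.**
- True HR 1.0, undated 20% MSS vs 5% HE: HR 0.75, type I error 19%.
- True HR 1.0, undated 10% in both arms: type I error 4.5%.
- True HR 1.9, HE median 35 days: 20% MSS vs 10% HE gives HR 1.26; 10% MSS vs 20% HE gives 2.01.

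**The case against.** The strongest reply is that the affected patient may not exist. The SAP does not say that opioid status was recorded separately from the stop date. If the form required a date whenever a patient said they had stopped, the two definitions are the same and nobody is misclassified. How the question was asked is data collection, which a SAP may leave to the protocol, and the protocol is not at hand. This stands, and it means that no size can be asserted.

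It also stands that the weeks 2, 4, 8 and 12 schedule is borrowed from the psychological measures. Opioid contacts may have been more frequent, which would make a forgotten date less likely. Holding every undated stopper to day 84 is one end of the range: censoring runs to last known contact, which may come soon after the stop, and the loss is then far smaller.

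A reader might infer three stronger things, none of which the SAP supports:
- **That the comparison was in fact weakened.** This needs a count of undated stops, and none is given.
- **That the false-positive rate is inflated.** This needs date reporting to differ between arms. Nothing suggests that it did, and equal rates leave type I error near 5%.
- **That the logistic model miscounts known stoppers.** This holds only if it uses the same event flag, and its coding is not stated.

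What the reply does not remove is the rule itself. It is stated, leaves no alternative route to an event, and gives the wrong result for any undated stop.

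**Conclusion.** The point holds as a defect in the event definition. A known but undated stop is treated as use up to last contact. That censoring is informative: it attenuates the hazard ratio at equal rates and could bias it either way at unequal rates.

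The size is unknown and may be zero. Under the stated assumptions, 10% undated stops give an HR of about 1.65 to 1.9 and power of about 0.53 to 0.74, the ends being day-84 censoring and censoring at the first visit after the stop. At 2% with day-84 censoring the HR is 1.86 and power about 0.71. The undated share, HE median, contact days and allocation ratio are all assumptions. The direction at equal rates follows from the rule when MSS patients stop faster; the figures only illustrate a range.

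**What to change.** - Define cessation as either a stop date given by the patient, or a report of no current use at a contact that follows a report of use.
- For an undated stop, set the time to the midpoint between the last contact with use and the first without. Repeat the Cox analysis with interval-censored times as a check.
- State that the logistic model counts these patients as ceased.
- Report the number of undated stops by arm.

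Where opioid status was recorded at each contact, the cost is SAP wording, recoding of existing responses and a few days of timing error for the patients concerned. If it was not recorded, the bracketing cannot be done, and the SAP should say so and state whether a date was required. If no stop was undated, the results do not change.

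### Should the Cox model for opioid cessation have been adjusted for the psychological scores measured before surgery?

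*SAP*

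**What the plan says.** Under Statistical Analysis, the main analysis of opioid cessation compares the psychological intervention (MSS) with the health education control (HE) by Kaplan-Meier curves, a log-rank test and a Cox model: "Time to opioid cessation event was assessed using a Cox proportional hazard regression model with the experimental condition as the predictor". No other term is named.

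The same section lists six patient-reported scores: anxiety, depression, pain catastrophizing, physical function, and the intensity and interference of pain. It calls them covariates but analyses them as outcomes, in a mixed ANOVA with treatment, "time (pre vs post, within-subjects), and the treatment time interaction as predictors". Each score therefore has a value from before surgery.

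Under Power Analysis, "The study was designed to detect a hazard ratio of 1.9" by Cox regression, and the result is "a total sample of 82 patients would be needed to yield a power of 0.8 and a two-tailed alpha of 0.05". No covariate is mentioned there either.

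**The concern.** Adjusting for a strong prognostic baseline variable usually raises the power of a time-to-event comparison. This trial is small, with 82 patients and a target power of 0.8, so even a few points would count. The data appear to be in hand already, and the label covariates invites the question why none is used as one. Pain or catastrophizing before surgery might plausibly predict how long a patient stays on opioids. If so, the plan would be giving up power at the cost of one line of code.

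**Working it through.** **1. Does the model match the sizing?** Inputs from Power Analysis: hazard ratio 1.9, power 0.8, two-sided 5% level. Equal arms are assumed.

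- Schoenfeld: 4 × (1.960 + 0.842)² / (ln 1.9)² = 31.40 / 0.412 = 76.2, rounded up to 77 events. Then 77 / 82 = 0.94, so 82 patients suffice if about 94% stop opioids.
- Freedman: (2.9 / 0.9)² × (1.960 + 0.842)² = 10.38 × 7.85 = 81.5, rounded up to 82 events. This equals the stated 82 if every patient has the event.

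Both are two-group calculations with no covariate. The Cox model under Statistical Analysis is the analysis that was sized.

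**2. Is the unadjusted test valid?** The title describes "A Randomized Controlled Pilot Study of a Pre-surgical Psychological Intervention". Under randomisation and non-informative censoring, leaving out a prognostic variable does not make the test invalid. Simulated type I error was 4.7 to 5.4% unadjusted, 5.0 to 5.7% with one score and 5.3 to 5.5% with two.

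**3. What could adjustment gain?** The SAP gives neither event rates nor prognostic strength, so both are assumed. Taking 76.2 / 82 = 0.929 as the overall event share, control cessation p solves (p + 1 − (1 − p)^1.9) / 2 = 0.929. This gives p = 0.877, and 98% in the MSS arm. The simulation used 41 per arm, exponential times, censoring at day 84, 10,000 runs per setting, and one standard normal score taken before the intervention. The conditional hazard ratio was set so that the unadjusted one is 1.9.

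| Assumed log-HR per SD of score | No loss to follow-up: unadjusted → adjusted power | 20% loss: unadjusted → adjusted power |
|---|---|---|
| 0 | 79 → 79% | 77 → 76% |
| 0.1 | 78 → 79% | 76 → 76% |
| 0.2 | 79 → 81% | 76 → 78% |
| 0.3 | 78 → 83% | 76 → 81% |
| 0.5 | 79 → 89% | 76 → 87% |

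At 0.2 and below the gain is about 2 points or less.

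**4. What if the score was taken after the intervention?** The intervention takes place before surgery, and the SAP counts time from surgery. A value from before surgery could therefore already reflect MSS. Adjusting for it would then remove part of the treatment effect. With the total effect held at 1.9 (no loss, 6,000 runs) and unadjusted power of 78 to 80%, adjusted power was:

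| Score already improved by MSS | log-HR 0.3 | log-HR 0.5 |
|---|---|---|
| 0.1 SD | 79.6% | 84.6% |
| 0.2 SD | 75.4% | 79.0% |
| 0.3 SD | 70.9% | 73.0% |
| 0.5 SD | 60.7% | 54.6% |

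The gain is gone at a shift of about 0.1 SD (log-HR 0.3) or 0.2 SD (log-HR 0.5). In the worst case shown, the loss is about 79 − 55 = 24 points.

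**5. What if some scores are missing?** PROC PHREG drops patients with a missing covariate by default. With scores assumed missing at random and a complete-case fit (no loss, 4,000 runs):

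| log-HR per SD | Unadjusted | Adjusted, 0% missing | 5% | 10% | 15% |
|---|---|---|---|---|---|
| 0 | 79.0% | 78.5% | 76.5% | 73.6% | 72.2% |
| 0.2 | 78.3% | 80.5% | 78.4% | 75.4% | 73.7% |
| 0.3 | 77.6% | 83.0% | 80.2% | 78.7% | 75.5% |
| 0.5 | 78.4% | 89.0% | 87.1% | 85.6% | 82.7% |

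At 10% missing, a score with log-HR 0.3 gains 78.7 − 77.6 = 1.1 points, and one with log-HR 0.2 loses 78.3 − 75.4 = 2.9 points.

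**6. Could the change still be made in advance?** The SAP is written in the past tense and already reports an interim step of the analysis: "and finding none, we averaged the postsurgical measures". Covariates chosen at this stage could not be shown to have been chosen blind to the results.

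**The case for a change.** The best case for adjustment is that a strong predictor makes a real difference. At a log-HR of 0.5 per SD the gain is about 10 points.

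The case is stronger still if 1.9 is read as the conditional hazard ratio, the effect at a fixed value of the score. With 90% control cessation and 3,000 runs per setting, unadjusted power is then 75% at log-HR 0.3 and 65% at 0.5. Adjustment brings these to 80% and 79%. The possible problem of a score taken after the intervention could be met by adjusting only if the value precedes it.

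This stands as a general argument for efficiency, but it does not show a fault in this plan. Power Analysis names no covariate, so the natural reading of 1.9 is the unadjusted hazard ratio. Nothing in the SAP shows that any of the six scores predicts cessation. The timing of assessments is a matter commonly left to the protocol, which is not at hand, so its absence here is no gap. Adjustment also has a price: the target becomes a conditional hazard ratio, missing scores need a rule, and the proportionality check must cover the added terms.

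**Conclusion.** The concern does not hold. The SAP fits the covariate-free comparison that it sized, the test is valid, and nothing in the document promises or requires adjustment. With 1.9 as the unadjusted hazard ratio, adjustment would change power by about +10 points at best, by 2 or less for a weak predictor, and by about −24 in the worst case examined. These figures rest on equal arms, exponential times, the assumed cessation rates and assumed prognostic strengths. The document settles neither the strength of any score nor its timing relative to the intervention. Because analysis had already begun when this text was written, the unadjusted model should remain the main analysis in any case. An adjusted fit would be a sensitivity analysis and would add no power to the main result. Leaving the scores out is a legitimate choice between two valid analyses.

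### The follow-up comparison of median time to opioid cessation uses a test with no place for censoring, on an outcome the SAP defines as right-censored

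*SAP*

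**What the plan says.** All of this is in the Statistical Analysis section of the SAP, apart from the design effect.

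- **Event:** "The opioid stop event was considered to have occurred if the patient reported an opioid stop date and was censored otherwise".
- **Duration:** days from surgery to the reported stop date or, failing that, to "last known patient contact (for censored observations)". A censored time can therefore fall well before week 12.
- **Main analysis:** "The effect of the MSS vs HE control on opioid cessation in the 12-week postsurgical follow-up period was assessed using survival analyses". The tools are "Product-limit survival estimates (Kaplan-Meier curves) and the log-rank test of equality of survival curves", from PROC LIFETEST, and a Cox model.
- **Follow-up analyses:** the first is a logistic regression on whether the patient stopped. For the second, "Second, we tested whether the median time to opioid cessation was different between the two groups using a nonparametric test of medians", by "PROC NPAR1WAY with the median option".
- **Design effect (Power Analysis section):** "The study was designed to detect a hazard ratio of 1.9", with 82 patients, power 0.8 and two-tailed alpha 0.05.

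The SAP does not say how censored patients enter the median test. It gives no loss or cessation rates.

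**The concern.** A median-score test asks of each patient only whether a single number lies above or below the pooled median. It has no event indicator, so it cannot carry the censoring that the same section has just defined. There are two ways to run it.

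- **(a) All patients enter.** A patient whose contact ends before the pooled median is scored as having stopped opioids that day. Medians are pulled down, and the arm that loses more contact early appears to stop sooner. There is no bias if follow-up is complete and the median lies before day 84, because every censored time then sits above the median.
- **(b) Only stop dates enter.** The comparison is among stoppers, a subgroup defined after randomisation. It is valid as a conditional description. It is not the median time to cessation of the two arms, even with complete follow-up.

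The p-value, and any medians quoted with it, therefore depend on an unstated choice. They can disagree with the Kaplan-Meier curves and log-rank test on the same data for that reason alone.

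**Working it through.** **The plan's own figure.** For HR 1.9, two-tailed 0.05 and power 0.8, (z sum)² = (1.960 + 0.842)² ≈ 7.85.

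- Freedman: (2.9/0.9)² × 7.85 ≈ 81.5, so 82 events.
- Schoenfeld: 4 × 7.85/(ln 1.9)² ≈ 76.2, so 77 events.

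The stated 82 is reproduced by Freedman if every patient stops, or by Schoenfeld at about 94–95% stopping. This matters below as the only hint of the cessation rate assumed at design.

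**Inputs.** From the SAP: HR 1.9, N = 82, 12 weeks (84 days). Assumed: 41 per arm; exponential times; control cessation by day 84 (F) of 60/70/80%, extended to 90–95%; loss of contact unrelated to outcome and uniform over days 0–42 or 0–84.

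**Reading (b), no loss, HR 1.9.** Control rate λ = −ln(1 − F)/84; the MSS rate is 1.9λ. The true median is ln 2/rate. The stoppers-only median is −ln(1 − F₈₄/2)/rate, where F₈₄ = 1 − exp(−84 × rate). For F = 60%, λ = 0.01091:

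- Control: true 0.693/0.01091 = 63.5 days; stoppers −ln(0.70)/0.01091 = 32.7 days.
- MSS: rate 0.02073, F₈₄ = 0.825; true 33.4 days; stoppers −ln(0.588)/0.02073 = 25.6 days.

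| Control cessation | True medians, MSS vs control | Stoppers-only medians | True gap | Stoppers-only gap |
|---|---|---|---|---|
| 60% | 33.4 vs 63.5 | 25.6 vs 32.7 | 30 | 7 |
| 70% | 25.5 vs 48.4 | 21.9 vs 30.1 | 23 | 8 |
| 80% | 19.0 vs 36.2 | 17.8 vs 26.7 | 17 | 9 |
| 90% | 13.3 vs 25.3 | 13.1 vs 21.8 | 12 | 9 |
| 95% | 10.2 vs 19.4 | 10.2 vs 18.1 | 9 | 8 |

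Simulated power at 60/70/80% (10,000 trials each) is 11/16/24%, against 69/74/78% for log-rank. Type I error is about 5%.

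**Reading (a), no loss.** There is no bias. Power is 59/59/60%. Type I error is about 8% because the scores are coarse. With 41 per arm the variance of the count above the median is 41 × 41 × 0.25/81 = 5.19, so the 1.96 limit is 4.46. The first attainable deviation beyond it is 4.5 (a count of 16 or 25 against 20.5), and the exact two-sided probability is 7.7%. This takes the normal approximation without continuity correction.

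**Reading (a), 20% loss in both arms.** The large-sample median solves exp(−λt) × (1 − 0.2·min(t/M, 1)) = 0.5, with M the last day of the loss window. Control medians become 43.1/35.5/28.6 days (M = 42) or 51.5/41.2/32.0 (M = 84), against a true 63.5/48.4/36.2. Simulated power at HR 1.9:

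| Loss window | Median test, all patients | Log-rank |
|---|---|---|
| None | 59/59/60% | 69/74/78% |
| Days 0–42 | 39/44/47% | 63/69/73% |
| Days 0–84 | 47/51/52% | 64/71/74% |

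Log-rank also loses power. From these rounded figures, the extra loss is 20 − 6 = 14, 15 − 5 = 10 and 13 − 5 = 8 points for early loss, and 12 − 5 = 7, 8 − 3 = 5 and 8 − 4 = 4 points for loss over the whole period.

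**Reading (a), no true effect, unequal loss.** Rejection rates at 60/70/80% cessation:

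| Loss by arm | Days 0–42 | Days 0–84 |
|---|---|---|
| 30% vs 10% | 25/20/16% | 14/12/10% |
| 20% vs 10% | 12/11/9% | 9/8/9% |
| 10% vs 5% | about 8–9% | about 8–9% |

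Log-rank rejects about 5% at 30% vs 10%. In that scenario, at 60% cessation, typical medians are 36 vs 54 days (0–42) or 47 vs 57 days (0–84), although both true medians are 63.5.

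**Independent check.** Separate simulations (4,000 trials each, loss over days 0–84) point the same way. With a true median of 40 days in both arms and loss of 50% vs 10%, the all-patient test gave medians of 29.6 vs 37.8 days and rejected 16.5% (7.5% without loss). Kaplan-Meier gave 41.0 vs 40.7 days, and log-rank rejected 5.2%.

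**The case against.** The strongest reply is that 60–80% control cessation is not what the design implies. Getting 82 patients from HR 1.9 needs about 94–100% of patients to stop, hence about 90% or more in control. At 90–95% the problem is smaller. The stoppers-only gap is about 9 days against a true 12, or 8 against 9, and stoppers-only power is 35–44%. Under 30% vs 10% early loss the all-patient test rejects about 10–12%, against a baseline of about 7–8%. This stands, and those rates belong in the range. It does not clear the test. With a control median of 20 days (cessation 1 − 2^(−84/20) = 94.6%) and no loss, simulated power is 41% for stoppers only, 58% for all patients and 80% for log-rank.

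Other points on that side:

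- The 25% figure needs threefold unequal loss, all early, at the lowest cessation rate. True; it is the upper end of the range, and small or late imbalance adds essentially nothing to the baseline.
- The two follow-up analyses could be read as a pair: whether patients stopped, then when among those who did. Then the fault is a missing label. That is possible, but the SAP speaks of the two groups, not of stoppers.
- The SAP says a difference in medians was tested, not that published medians come from that step. True; only the p-value is certainly affected.
- Readings (a) and (b) are alternatives, so their harms do not add.

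**Conclusion.** The point holds and should be fixed. A test with no event indicator is applied to a right-censored duration, and neither way of running it generally answers the question posed. Under reading (b) it misses the target even with complete follow-up: a true gap of 30 days reads as 7 at 60% control cessation, and 12 as 9 at 90%, with power far below log-rank throughout. Under reading (a) it is unbiased with complete follow-up and a median before day 84. With unequal early loss it rejects too often, from essentially its 8% baseline up to 25% in the worst case examined.

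These sizes rest on exponential times, 41 per arm, loss unrelated to outcome, and assumed cessation and loss rates; the actual size is unknown. The Kaplan-Meier, log-rank and Cox analyses and the stated power are not affected, so the main inference stands.

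**What to change.** - Replace the NPAR1WAY median test with Kaplan-Meier medians and 95% confidence intervals by arm from the PROC LIFETEST run, on the same patients as the log-rank and Cox analyses. Keep log-rank as the between-arm test.
- State which patients entered the median test already run, and report the number and timing of losses by arm.
- If a median contrast is still wanted, give a bootstrap interval for the difference in Kaplan-Meier medians, labelled as a follow-up analysis. If a stoppers-only median is kept, label it as descriptive among stoppers.

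In the simulations at 60/70/80% cessation, the typical Kaplan-Meier control median stayed within 0.5 day of the truth at 20% loss under both timings.

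**Cost.** SAP wording and output from a procedure already run; no new data or patients. Because the SAP is written in the past tense, this is a disclosed correction, not a pre-specification. The control Kaplan-Meier median is not estimable in about 9–12% of simulated trials at 60% cessation (under 1% at 70–80%). The bootstrap contrast is conservative (null rejection 1–4%) and has power of only 34–49% at HR 1.9, which is why log-rank should remain the test.
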